### **1.1 Primary Objective**

- Characterise case-mix, processes of care and variations in nonoperative and operative management strategies, including emergency, ward, surgical and ICU care, in patients presenting with traumatic spinal injury (TSI) between centres across low and high Human Development Index (HDI) countries

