### 3.4 Duration of Study

Local study teams may pick any 30-day period between the 6-month study period to conduct the study. Teams must follow patients for up to 6-weeks post-admission or until they are discharged or die (whichever event occurs first). For example, if a team selects 1/6/2021 as their start date, they must include all patients who meet the inclusion criteria between 1/6/2021 and 30/6/2021. Moreover, if a patient is admitted during the inclusion period on 30/6/2021 they should be followed up until the 11/8/2021 or until discharge or death (whichever event occurs first).

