## **5. Statistical Analysis**

Anonymised data will be analysed by the central study team. Fundamentally the main analysis will consist of a quantitative description of case-mix and the variations in processes of care. Identification and description of areas where known best practice is lacking or unavailable will be performed. This will enable identification of potential targets for future implementation studies.

In addition, early outcomes will be assessed to identify case-mix and process factors that may form a substrate for intervention. Participating centres will be stratified based on their country into groups based on their Human Development Index (HDI). The Human Development Index is calculated for each country based on its life expectancy at birth, years of schooling and gross national income (GNI) per capita.

Specifically, after data validation and curation, the primary analysis will comprise of (1) statistical descriptive analysis of patient-level registry variables, (2) characterisation of processes of care using statistical descriptions of both provider profiling data and patient-level process variables followed by a description of typical process groupings. This will follow and extend methodologies that have previously been applied successfully to traumatic brain injury. Case-mix and process analysis will be stratified in a nested way by site, country, and association with human development index (HDI).

Analysis for the secondary objectives will consist of a quantitative statistical summary of non-operative and operative management. Intra- and inter-site variances will be compared and associations with HDI and process of care factors sought.

Whilst only short-term outcomes can be obtained in this pragmatic point-study, outcomes analysis will be attempted for early mortality, functional status as assessed using the 5-point Frankel Grade, neurology, adverse events and trajectory from admission to 6 weeks post-injury (or discharge or death, whichever occurs first). These will be analysed by HDI group in an appropriate nested model accounting for random effects of site and country. Either ordinal models (for statistical power) or dichotomised models will be used depending on the statistical properties of the data and suitability of model assumptions. Mixed effects models will be used to assess the relationship between HDI and deterioration in functional status at 6 weeks while controlling for confounding variables.

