
Associations between patient factors and processes of care will be sought with recognised indicators of evidence-based good practice to identify patient profiles associated with efficacious treatment trajectories. Using methodology previously successfully applied to TBI, process of care variables from both the registry and provider profiling will be collated with estimates of variability to inform a future Delphi consensus process aimed at defining process of care performance indicators that are feasible, measurable, and globally relevant.

Provider profiling summary statistics will be compared with current evidence-based best practice to identify gaps and associations with process of care, case-mix, site and HDI will be explored using standard statistical approaches. Variability in guideline availability and any association with TSI care will be assessed by comparing provider profiling and registry data using methodology conducted previously for TBI.

The data, along with catchment area data from provider profiling will be used to obtain point estimates with confidence intervals to provide a high-level description of the epidemiology of TSI across the sites studied using routinely available population data. A similar methodology that has been applied to the study of chronic subdural haemorrhage will be utilised.

A *p*-value of less than 0.05 will be considered statistically significant, correction for multiple comparisons will not be undertaken. A median odds ratio approach will be used to compare variations in outcomes between sites correcting for explanatory features discovered in the descriptive part of the analysis.

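### Between-centre variation in care is a primary objective, yet the plan names an estimator that removes sampling error for outcomes only, not for patient-level processes of care

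*Combined protocol and SAP*

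**What the plan says.** Section 1.1 (Primary Objective) sets out to "Characterise case-mix, processes of care and variations in nonoperative and operative management strategies" between centres in low and high HDI countries.

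Section 5 (Statistical Analysis) meets this with description. It states that "the primary analysis will comprise of (1) statistical descriptive analysis of patient-level registry variables", followed by a description of care processes from provider profiling and patient-level variables and a grouping of typical processes. Then: "Case-mix and process analysis will be stratified in a nested way by site, country, and association with human development index (HDI". For these variables it names no model, interval, shrinkage, case-mix adjustment or rule for small sites.

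Section 5 does name methods that separate true site differences from sampling error, but attaches them to outcomes. After listing the early outcomes it says: "These will be analysed by HDI group in an appropriate nested model accounting for random effects of site and country". Later it says: "A median odds ratio approach will be used to compare variations in outcomes between sites".

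Two sentences in section 5 come closer to processes of care. Under the secondary objectives, for operative and non-operative management: "Intra- and inter-site variances will be compared and associations with HDI and process of care factors sought". As input to a later Delphi exercise: "process of care variables from both the registry and provider profiling will be collated with estimates of variability". Neither names an estimator.

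On site size, section 3.4 says: "Local study teams may pick any 30-day period between the 6-month study period to conduct the study". Section 3.1.1 admits institutions of every level and sets no minimum caseload. No sample size, number of sites or expected patients per site is given.

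**The concern.** An observed site proportion is the site's true rate plus binomial error. When sites contribute few patients, proportions spread widely even if every site treats alike, so the spread overstates real differences in practice. A variance model with a site random effect estimates the real part. The plan has such a model, but assigns it to outcomes, which are a secondary objective, and not to the between-centre variation in care that is primary.

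At stake is how the main result can be read. Process variability will feed the Delphi work on performance indicators (section 5), and local teams will compare their own practice with international practice (section 8.1). Without an estimate of true between-site variance, a reader of the site strata cannot tell large practice variation from small samples.

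**Working it through.** The plan states no sample size or precision figure, so there is none to reproduce. What follows is a sensitivity calculation for a binary patient-level process variable.

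**Inputs**
- From the documents: a 30-day window per site (section 3.4) and no minimum caseload (section 3.1.1).
- Assumed: n = 5 to 50 patients per site, equal across sites; process rate at the median site 10%, 30% or 50%; site effects normal on the logit scale; true MOR 1.25 to 4.

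**One site.** With 5 of 10 patients receiving a process, the Wilson 95% interval is 0.5 ± 1.96 × √(0.25/10 + 1.96²/(4 × 100)) / (1 + 1.96²/10) = 0.5 ± 0.263, or 24% to 76%.

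**No true differences (benchmark only).** With 100 sites all at a true rate of 50% (MOR 1.0), the median lowest and highest observed site rates in simulation are:

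| Patients per site | Lowest | Highest |
|---|---|---|
| 5 | 0% | 100% |
| 10 | 10% | 90% |
| 20 | 25% | 75% |
| 30 | 27% | 73% |

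This shows how wide pure noise can look. It does not show what share of the spread in this study would be noise.

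**Chance share of the observed variance.** Let p be a site's true rate.
- Site standard deviation on the logit scale: τ = ln(MOR) / (√2 × 0.6745) = ln(MOR) / 0.954.
- Chance share = (E[p(1−p)]/n) / (E[p(1−p)]/n + Var(p)).

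Example: MOR 2, median rate 50%.
- τ = 0.693/0.954 = 0.73. The standard deviation of p is 0.163, so Var(p) = 0.0266.
- The mean of p is 0.5 by symmetry, so E[p(1−p)] = 0.25 − 0.0266 = 0.2234.
- n = 10: 0.02234 / (0.02234 + 0.0266) = 46%.
- n = 5: 0.04468 / (0.04468 + 0.0266) = 63%.
- n = 50: 0.00447 / (0.00447 + 0.0266) = 14%.
- n = 20 and 30 give 30% and 22%.

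Chance share at an assumed 10 patients per site:

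| True MOR | Rate 50% | Rate 30% | Rate 10% |
|---|---|---|---|
| 1.25 | 88% | 90% | 95% |
| 1.5 | 70% | 73% | 85% |
| 2 | 46% | 48% | 63% |
| 2.5 | 34% | 36% | 47% |
| 3 | 27% | 29% | 37% |
| 4 | 20% | 21% | 26% |

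Chance and true variance are equal at n = E[p(1−p)] / Var(p). That is about 23 (rate 50%) to 56 (rate 10%) patients per site at MOR 1.5, between 8 and 9 (rate 50%) to 17 (rate 10%) at MOR 2, and about 4 to 6 at MOR 3.

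**The case against.** The best defence is that the plan already intends to do this. Comparing variance within and between sites is the standard way to separate chance from real differences, and section 5 promises that comparison for management. It also promises measures of variability for process variables, and says it will follow and extend methods used in traumatic brain injury. The Background expects variation in care to be substantial, so a high true MOR is plausible, and there chance is the smaller part.

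Much of this stands. The intent is stated, and it would be wrong to say that the plan ignores the matter. What is missing is the estimator. A variance computed from observed site proportions still contains sampling error. The management comparison also sits under the secondary objectives, and the content of the cited methods is not in the documents.

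Three stronger readings are tempting, and the documents do not support them:
- **That site differences will be mostly chance.** No caseload per site is given. At an assumed 10 per site this holds for a true MOR of 1.5 or less, is near even at MOR 2 for rates of 30% to 50%, and fails at MOR 2.5 or more.
- **That only unmodelled site tables will be produced.** The plan says the analysis is stratified; it does not exclude modelling.
- **That outlying centres or countries will be picked as targets.** Section 5 defines targets as areas where known best practice is lacking or unavailable, which is comparison with a standard. The calculation covers single sites, not country or HDI strata that may pool several.

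Provider-profiling items have one response per institution, so patient sampling error does not arise there.

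**Conclusion.** The concern holds as a gap in specification, confined to patient-level process variables. The primary objective asks about between-centre variation in care, while the only named methods that remove sampling error from such variation are reserved for outcomes.

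Its size cannot be fixed from the documents. Across the assumed range at 10 patients per site, chance accounts for anything from 20% to 95% of the observed between-site variance. The result rests on binary process variables, equal site sizes and logit-normal site effects; caseload, process rates and true MOR are all assumptions. That width is itself the argument for a variance model: site-stratified description alone would not show where in the range the study lies. The change should be made, as a cheap improvement.

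**What to change.** In section 5, extend the planned nested model to a short, pre-listed set of key patient-level process variables:
- Fit a random-intercept model with site nested within country.
- Report the MOR with its 95% confidence interval, first unadjusted, then adjusted for baseline variables already in Appendix A, such as age, injury mechanism, GCS, Kampala Trauma Score, Frankel grade at initial assessment and AO classification.
- Show shrunken site estimates with intervals, and keep the site-stratified tables as a supplement.
- Name this model as the estimator behind the promised variance comparison and measures of variability.
- State the expected range of patients per site.

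Provider-profiling items can stay descriptive.

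No new data are needed, and the methods are already in the plan for outcomes. The cost is one more model per process variable, fitted unadjusted and adjusted, and very small sites will be pulled toward the mean.

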## **6. Limitations**

This pragmatic, prospective, observational study has been designed with the aim of obtaining estimates of the current global case-mix, management and processes of care for patients who present with TSI at a single point in time. Long-term follow-up is therefore not appropriate or feasible across all settings. This protocol has not been designed to investigate or provide:

- Worldwide epidemiological data of all TSI
- Indications for or efficacy of specific management for patients with TSI
- Long-term outcomes following TSI

## **7. Approval**

GNOS Spine will not collect any patient identifiable data, with all data entered directly into an anonymised form on our secure, online platform. The aim of GNOS Spine is to measure current practice worldwide, with no intended changes to standard management of TSI to be introduced using the findings of this study.

The United Kingdom National Health Service Health Research Authority tool classifies this study as service evaluation, rather than original research, and hence, it does not require formal approval by a Research Ethics Committee with the United Kingdom. This has been confirmed by the South East Scotland Research Ethics Service.

Local teams should follow local protocol and guidance to obtain approval from either their service evaluation, clinical audit, research department or head of department, prior to commencing any data collection for this study. Where local institutions require approval from their Research Ethics Committee, we would advise seeking an expedited review or ethical waiver if deemed appropriate locally, in view of only anonymised routine clinical data being collected. Written confirmation will be requested from each institution before local study teams are able to access the online, data-collection platform.

If classified locally as research, local study teams should follow local protocol, which may involve consenting all patients involved to participate in this study. Example participant information leaflets and participant consent forms can be found on the study website ([www.globalspinetrauma.com](http://www.globalspinetrauma.com)) or requested via email ([[contact]](mailto:[contact])). These are available in English, and so should be translated where required.

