##### **3.1.2 Patient inclusion and exclusion criteria**

###### **3.1.2.1 Inclusion Criteria**

All adult patients presenting to the participating institution with a first presentation of TSI confirmed radiographically, during the selected 30-day inclusion period are eligible for inclusion in the core study.

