### 4.2 Data Validation

A number of steps have been taken to ensure validation of all data entered.

- I. The dataset, web-based case report forms, and curation process has been designed according to DAQCOR principles.
- II. Web-based forms in the ORION platform contain fixed options at the point of data entry to maximise the likelihood of accurate and complete data capture at the point of collection.
- III. A local data validator independent to the local study team will be appointed at every participating institution. They will have access to a separate platform on Orion to ensure blinding to the rest of the data collected at their institution. They will be asked to complete a two-phase validation process, with a specific ORION validation user guide available to guide them through the process.
  - a. Prospective Case Acquisition: During the selected 4-week inclusion period, the local data validator will be asked to independently identify and collect all patient cases suitable for inclusion in the study. For validation, they will be required to prospectively collect these cases, recording the admission date, age at admission and AO injury type. This will subsequently be correlated with the data collected by their local team by the central study team.
  - b. Retrospective Operative Data: At 10 weeks from the start of the inclusion period (6-weeks following the end of the inclusion period), the local data validator will be asked to independently access operating theatre logs over the preceding 10 weeks. They will be required to document all the patients who have had an operation for TSI during this period and input the date and type of operation into the validation system where this corresponds to a patient admitted during the inclusion period. This will be used by the central study team to validate this specific cohort of their institution's cases.

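### Mixed local consent rules may select patients differently between sites, and the plan does not say it will record or analyse the consent model

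*Combined protocol and SAP*

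**What the plan says.** The target population is complete. Section 3.1.2.1 takes in "All adult patients presenting to the participating institution with a first presentation of TSI confirmed radiographically, during the selected 30-day inclusion period", and Section 3.4 tells a team starting on 1 June that "they must include all patients who meet the inclusion criteria between 1/6/2021 and 30/6/2021". Consent is not an inclusion criterion. Neither of the two exclusions in Section 3.1.2.2 concerns death before consent, incapacity or refusal.

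Section 7 then lets the route to enrolment vary. Teams are to "obtain approval from either their service evaluation, clinical audit, research department or head of department", with no individual consent mentioned for audit or service evaluation. For research sites the text reads: "If classified locally as research, local study teams should follow local protocol, which may involve consenting all patients involved to participate in this study". Where ethics committee approval is required, the authors add that "we would advise seeking an expedited review or ethical waiver if deemed appropriate locally". Template consent forms are offered. Section 7 also says: "Written confirmation will be requested from each institution before local study teams are able to access the online, data-collection platform".

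Section 5 describes case-mix by site, country and HDI. Of the outcomes, including early mortality, it says: "These will be analysed by HDI group in an appropriate nested model accounting for random effects of site and country". It also plans a median odds ratio for variation between sites.

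Under Section 4.2 a local validator at every institution is asked to "independently identify and collect all patient cases suitable for inclusion in the study", noting admission date, age and AO injury type. The central team compares that list with the site's own data.

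**The concern.** A registry of consecutive patients supports comparisons between sites only if sites capture their patients in the same way. Here one site may enter everyone while another enters only those from whom consent was obtained. The data set itself shows that patients who are hard to consent belong to the cohort: Appendix A records intubation, GCS, major intracranial injury, ITU admission, transfer to another hospital and death.

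If non-enrolment at consent sites is related to severity or survival, differences between sites in case-mix and mortality will partly reflect enrolment rules. The consent model appears in no field of Appendix A or the Appendix B registration form, nor among the profiling topics listed in Section 3.2, the analyses in Section 5 or the Limitations in Section 6. As written, a reader of the results could not tell which sites enrolled under which rule.

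**Working it through.** The documents give no mortality rate, consent rate, number of consent sites or sample size, so there is no figure in the plan to reproduce. Every rate below is an assumption, chosen to show range and direction.

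**Step 1: one consent site against one full-inclusion site.** Let m be true mortality, the same at both sites. Let d and s be the shares of deaths and of survivors not enrolled at the consent site.

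- Observed mortality = m(1−d) / [m(1−d) + (1−m)(1−s)]
- Spurious odds ratio = (1−d)/(1−s); m cancels, so it does not depend on baseline mortality

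With m = 8%:

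| Survivors lost (s) | Deaths lost (d) | Observed mortality | Spurious odds ratio |
|---|---|---|---|
| 10% | 25% | 0.060/(0.060+0.828) = 6.8% | 0.75/0.90 = 0.83 |
| 10% | 50% | 0.040/(0.040+0.828) = 4.6% | 0.50/0.90 = 0.56 |
| 10% | 75% | 0.020/(0.020+0.828) = 2.4% | 0.25/0.90 = 0.28 |
| 20% | 20% | 0.064/(0.064+0.736) = 8.0% | 0.80/0.80 = 1.00 |
| 25% | 10% | 0.072/(0.072+0.690) = 9.4% | 0.90/0.75 = 1.20 |

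The last row is plausible where refusals, or mild injuries discharged before anyone asks, make up most of the loss. The direction is therefore not fixed.

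**Step 2: HDI groups.** Let c be the share of a group's patients who are at consent sites. With the same true mortality everywhere, the group's odds of death are multiplied by (1−cd)/(1−cs). Take d = 50% and s = 10%:

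- c = 20%: 0.90/0.98 = 0.918
- c = 60%: 0.70/0.94 = 0.745
- c = 80%: 0.60/0.92 = 0.652

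The spurious odds ratio for low against high HDI is then:

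- equal c in both groups: 1.00
- 20% in high, 60% in low: 0.745/0.918 = 0.81
- 20% in high, 80% in low: 0.652/0.918 = 0.71
- 60% in high, 20% in low: 0.918/0.745 = 1.23

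These are crude pooled ratios, not estimates from the planned mixed model. They show that the mortality contrast between HDI groups is affected only if consent practice differs between the groups.

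**Step 3: the random site effect.** Suppose there is no true variation between sites and a share c of sites loses patients as in the second row of the table (odds ratio 0.556). The variance of the site log-odds is v = (ln 0.556)² × c(1−c), and the median odds ratio is exp(0.6745 × √(2v)).

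- c = 20%: v = 0.055, median odds ratio 1.25
- c = 50%: v = 0.086, median odds ratio 1.32

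This treats a two-point distribution as normal, so it is approximate. It shows that the random effect absorbs the selection as apparent site variation. Adjustment for patient factors cannot restore patients who were never entered.

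**Step 4: the validator's list.** Set against the site's own data, it can reveal a shortfall and a skew in age or AO type. It carries no vital status, GCS or Frankel grade, so it cannot show whether the missing cases are deaths. Section 4.2 does not say whether a validator at a consent site may list unconsented patients, or how a mismatch is used.

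**The case against.** The strongest reply is that this is a conditional risk and not a demonstrated bias. Four stronger readings are tempting, and the documents do not support them.

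- *That some sites must obtain consent.* Section 7 says only that local protocol may involve it, and advises expedited review or a waiver where appropriate. The number of sites affected, if any, is unknown.
- *That patients who die early are lost.* No passage excludes them. The documents are silent on relatives' or deferred consent, which local rules might allow.
- *That consent sites will show lower mortality.* This holds only if deaths are lost more often than survivors; the last two table rows show no effect and the reverse.
- *That HDI comparisons are biased, and that the data could not reveal it.* Consent rules set by country or institution need not be associated with HDI. The validator's list could also expose missing cases.

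It is also fair to say that the main analysis is descriptive and that Section 5 promises only to attempt outcome analysis.

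All of this stands as a limit on the claim, but it does not remove the point. Case-mix is part of the primary objective, so a descriptive analysis is exposed too. The validator is a partial safeguard that does not reach vital status. Nothing in the plan says that the consent model will be recorded or used.

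**Conclusion.** The plan permits enrolment rules that differ between sites, aims at all eligible patients, and compares sites and HDI groups without saying that it will record or analyse the difference. The result is a possible differential selection of unknown size and direction. Over the assumed rates the spurious mortality odds ratio between sites runs from 0.28 to 1.20, and it is 1.00 when loss is unrelated to outcome. Distortion of between-site comparisons requires non-enrolment at consent sites to be related to severity or outcome. Distortion of the HDI mortality comparison requires, in addition, that consent practice differ by HDI group, on which the documents say nothing. The point is worth acting on because the remedy is cheap and the count of non-enrolled patients is hard to reconstruct afterwards.

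**What to change.** Leave local consent rules as they are, and make these changes:

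1. Record each site's consent model (none or waiver, opt-out, individual consent), taken from the written confirmation that Section 7 already requests. Ask sites to state it there.
2. Where local rules allow, keep an anonymous aggregate count of eligible patients not enrolled, by reason (died before approach, lacked capacity, declined, left before approach) and by vital status.
3. In Section 5, report case-mix and the HDI models for mortality and Frankel grade with and without individual-consent sites, or with consent model as a site-level covariate.
4. In Section 4.2, report unconsented cases as a separate category by consent model. They should not count as data-collection misses. They should not be dropped either, because that would hide the only built-in signal of the loss.
5. Add the issue to Section 6.

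The cost is one site-level field, one tally at consent sites, one sensitivity analysis and two short text changes. Intervals will be wider when consent sites are left out, and the tally may itself need local permission.
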